At the final analysis time, a supportive analysis will adjust for cross-over from Control to Lutathera. This will be achieved by using a *rank-preserving structural failure time method (RPSFT)* to correct for confounding introduced by the change of treatment. The use of the RPSFT method allows survival time estimates gained by anyone receiving Lutathera (i.e. either as randomized to Lutathera or after cross-over from Control to Lutathera). The RPSFT model is based on an accelerated failure time model) and uses a structural assumption of time-proportionality instead of a proportional hazards assumption as used in the Cox model. The widely used Cox model measures drug effect on the hazard ratio scale, whereas the accelerated failure time model measures drug effect on the survival time ratio scale.

Additionally, a supportive analysis of OS based on the *Inverse Probability Censoring Weight* method will be performed at the final analysis time. Further details regarding theses analyses will be given in the SAP.

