2. Rank Preserving Structural Failure Time model (RPSFT), which uses an acceleration factor to adjust for any cross-over from Octreotide to Lutathera or for re-treatment of Lutathera for those in the investigational arm; this implies a modification of the

proportional hazards model, see [Section 5.4.1](#). This approach will be analyzed in the final study analysis, and not in the primary PFS analysis.

3. IPCW, which uses Inverse Probability of Censoring Weighting to adjust for any cross-over from Octreotide to Lutathera or for re-treatment of Lutathera for those in the investigational arm, see [Section 5.4.1](#). This approach will be analyzed in the final study analysis, and not in the primary PFS analysis.

ITT approach is primary. Approaches 2 and 3 are outside the scope of the primary analysis, and will be conducted in the final analysis. The analysis proceeds by Cox regression as in the primary analysis of PFS.

Reasons for censoring ('Alive' or 'Lost to follow-up') and death cause will be listed by treatment arm. Survival status, reason for censoring and death cause will be listed. Patients not known to have died will be censored for 'Loss to follow-up' if the time between their last contact date and the analysis cut-off date is longer than 12 months + 2 months window (i.e. the planned interval between two OS follow-up visits in follow up plus the 1-month window on either side).

Time to second progression (PFS2)

As additional exploratory end-point, the Time to Second Progression (PFS2) will be assessed in the two study arms. PFS2 is defined as the time from randomization to the first documented progression after the start of next-line anti-neoplastic therapy or death from any cause, whichever occurs first. The first documented progression on next-line treatment is based on investigator RECIST assessment of PD. It is recognized that the limitation due to potential cross-over or re-treatment and the lower scans frequency during follow-up will reduce the possibility to reach firm conclusions on PFS2.

- Next-line therapy is defined as the first new (systemic) anti-neoplastic therapy initiated after discontinuation of study treatment regardless of the discontinuation reason. Drugs given as part of the same regimen should be considered as one line (i.e., part of the next-line therapy).
- Re-treatment with Lutathera (additional cycles after completion of the 4 cycle treatment on study) will count as next-line anticancer therapy.

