5.4.3 Special statistical methods for OS analysis

Patients who progressed on Octreotide LAR are allowed to cross-over to open-label Lutathera. However, Octreotide LAR patients who switch to Lutathera after they progress are likely to benefit from the delayed administration of Lutathera and, therefore, the survival treatment estimate becomes confounded. Under such circumstances, the statistical test of the treatment effect is known to be biased towards the null hypothesis of no difference (Robins and Tsiatis 1991; Korhonen et al 1999; Greenland et al 2008).

However, with the inclusion of Lutathera re-treatment for some patients randomized in the Lutathera investigational arm, these patients may have increased OS compared to those who do not receive Lutathera re-treatment after central progression.

Therefore, the following modeling approaches will be used to obtain an estimate of survival treatment effect corrected for treatment cross-over and re-treatment: ‘Rank-preserving

structural failure time method' and 'Cox model with Inverse Probability of Censoring Weighting'. More details are provided in sections below. Should a patient have switched prior to progression (locally or centrally confirmed), that patient will be analysed similarly to those that switched after progression.

Despite the cross-over and re-treatment design, a supportive analysis of OS will use the strict intention-to-treat (ITT) approach, i.e., 'analyze as randomized' and ignore the treatment switch or re-treatment with Lutathera (and ignore additional anticancer therapies administered after study treatment discontinuation).

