5.4.3.1 RPSFT approach

The primary analysis of OS will be using *rank-preserving structural failure time method (RPSFT)* to correct for confounding introduced by the change of treatment (Robins and Tsiatis 1991; Korhonen et al 1999). The use of RPSFT method allows to estimate the survival time gained by anyone receiving Lutathera (i.e., either as randomized to Lutathera or after cross-over from Octreotide LAR to open-label Lutathera). The RPSFT model is based on an accelerated failure time model (Kalbfleisch and Prentice 2002) and uses a structural assumption of time-proportionality instead of a proportional hazards assumption as used in the Cox model. The widely used Cox model measures drug effect on the hazard ratio scale, whereas the accelerated failure time model measures drug effect on the survival time ratio scale.

Notation

We follow (Korhonen et al 1999) for the notation. The treatment assignment indicator is denoted by R_i and takes the value 0 if allocated to Octreotide LAR and 1 if allocated to active drug (Lutathera 10 mg). $Strata_i$ stands to baseline stratification factors. Each individual is followed from the time of randomization (DR_i) until death or the date of last contact (EOF_i) and the fixed closing date (CD_i) which ever comes first. The censoring time $C_i = \min(EOF_i - DR_i, CD_i - DR_i)$, is measured in days and is assumed to be independent of the treatment assignment. (Note: in a sensitivity analysis, censoring time $C_i = EOF_i - DR_i$ will also be considered). Time to death (T_i) is the time from randomization to death which is also measured in days. We can only observe $X_i = \min(T_i, C_i)$ with $\delta_i = 1$ if $X_i = T_i$ and $\delta_i = 0$ otherwise. Some of the subjects randomized to the Octreotide LAR arm switch to the active drug at some point after randomization. There may be several different periods when active drug has been received instead of the randomized Octreotide LAR. The total time from randomization to switch is denoted as A_i . If no switch occurs in the Octreotide LAR arm then $A_i = 0$. Switching to the active drug is potentially related to the patient's prognosis and thus cannot be assumed independent of the death time.

Thus, the observed data for each subject i are $\{R_i, Strata_i, C_i, X_i, \delta_i, A_i\}$.

Model

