$$\lambda(t | \bar{A}(t), V) = \lambda_0(t) \exp(\gamma_1 A_i(t) + \gamma_2 V_i); t \leq S_i$$

where a subject stays at risk for death until (s)he switches to the active treatment. Thus, the whole follow-up experience from randomization to $X_i = \min(T_i, C_i)$ is used from subjects randomized to the active treatment arm. But, in the Octreotide LAR arm only the follow-up experience from randomization to $\min(S_i, X_i)$ is used in the marginal structural Cox model. This

means in practice that in the Octreotide LAR arm the data after switching to the open label active treatment is discarded. Each subject is given in this model the case weight indicating the cumulative probability of not switching to the active treatment at time t . Unfortunately, the PROC PHREG procedure does not allow to specify time-dependent weights. Therefore one needs to divide the follow-up time into discrete time intervals and fit the above model using the PROC GENMOD procedure which allows time-dependent weights.

The case weights are estimated using the IPCW scheme for the probability of switching in the Octreotide LAR arm. In the IPCW, the probability of not switching is modeled using two separate logistic regression models as follows:

$$sw_i(k) = \prod_{u=0}^k \frac{\Pr(A_i(u) = a_i(u) \mid \bar{A}_i(u) = (0, \dots, 0)^T, V_i)}{\Pr(A_i(u) = a_i(u) \mid \bar{A}_i(u) = (0, \dots, 0)^T, V_i, \bar{L}_i(u))}$$
$$a_i(u) = \begin{cases} 1 & \text{if subject crossed - over at time } k \\ 0 & \text{if subject did not crossed - over at time } k \end{cases}$$

The first logistic regression model (i.e., the nominator model) uses only the baseline covariate information to describe the probability of switching. The second logistic regression model (i.e., the denominator model) uses both baseline covariate information and time-dependent covariate information. The estimation of these stabilized weights can easily be done with the PROC LOGISTIC procedure in SAS.

Note that the estimation of the stabilized weights is only needed in the Octreotide LAR arm. In the active treatment arm we set the stabilized weights to 1 for all subjects and for all discrete time periods.

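### The SAP contradicts itself and the protocol on which overall survival analysis is primary, and claims a re-treatment correction that neither adjusted method makes

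*SAP*

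**What the plan says.** **Which analysis is primary.** SAP 2.7.1 lists three approaches to OS: as-randomized (ITT), RPSFT and IPCW. It then says: "ITT approach is primary". The next sentence reads: "Approaches 2 and 3 are outside the scope of the primary analysis, and will be conducted in the final analysis". Protocol 12.5.2 analyses OS in the full analysis set by randomized arm. It adds: "At the final analysis time, a supportive analysis will adjust for cross-over from Control to Lutathera". That analysis is RPSFT, and the protocol also labels IPCW supportive.

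SAP 5.4.3 and 5.4.3.1 reverse the labels. In 5.4.3, "a supportive analysis of OS will use the strict intention-to-treat (ITT) approach". Section 5.4.3.1 opens with "The primary analysis of OS will be using" and names RPSFT. SAP Section 4, on changes to the protocol's analyses, is marked not applicable.

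**What the adjusted analyses correct for.** SAP 2.7.1 describes IPCW as a method "to adjust for any cross-over from Octreotide to Lutathera or for re-treatment of Lutathera for those in the investigational arm" and says the same of RPSFT. The introduction to 5.4.3 repeats the claim for both. The IPCW specification in 5.4.3.2 states: "In the active treatment arm we set the stabilized weights to 1 for all subjects and for all discrete time periods".

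**The concern.** Control patients may cross over to Lutathera after progression, and Lutathera patients may be re-treated. Whether the main OS analysis ignores these switches or models them determines the reported effect. It also changes the scale: 5.4.3.1 describes RPSFT as estimating a survival-time ratio, whereas the ITT analysis gives a Cox hazard ratio. A plan that gives the primary label to both leaves the main OS estimate undetermined.

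The second problem is one of description. An estimate reported as corrected for both kinds of post-progression Lutathera, when only control-arm cross-over was handled, would be mislabelled. SAP 5.4.3 itself says that re-treated patients may live longer as a result, so by its own reasoning the omission is not neutral.

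**Working it through.** **1. The plan's own figures.** The only sample-size figures are for PFS (protocol 12.8.1, SAP Section 3), and they reproduce.
- Events: (1.960 + 1.282)² / [(2/3)(1/3)(ln 0.5)²] = 10.51 / 0.1068 = 98.4, rounded up to 99.
- Critical hazard ratio: exp(−1.960/√(99 × 2/9)) = 0.658.
- Difference in medians: 15/0.658 − 15 = 7.8 months.

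None of these depends on the OS analysis, and the documents give no OS power or event figure to check.

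**2. The labels side by side.**

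| Source | ITT | RPSFT | IPCW |
|---|---|---|---|
| Protocol 12.5.2 | main analysis, as randomized | supportive | supportive |
| SAP 2.7.1 | primary | not primary, final analysis only | not primary, final analysis only |
| SAP 5.4.3 and 5.4.3.1 | supportive | primary | additional |
| SAP Section 4 | no change declared | no change declared | no change declared |

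**3. Whether the algorithms handle re-treatment.**
- IPCW (5.4.3.2): the stated purpose is to account for cross-over. The treatment indicator is 1 in every interval for the Lutathera arm, so re-treatment leaves no trace in the data. That arm contributes all its follow-up, weights are estimated only in the octreotide arm, and Lutathera-arm weights are fixed at 1. Re-treated patients are neither censored at re-treatment nor re-weighted.
- RPSFT (5.4.3.1): the exposure variable is the octreotide arm's time from randomization to switch. The observed data are arm, strata, censoring time, follow-up time, death indicator and that variable. There is no re-treatment term.

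**4. Illustration of size.** The PFS medians of 15 and 30 months and the 2:1 allocation come from the documents. The rest is assumed: control OS median 36 months, OS hazard ratio 0.70, a 30% lower death hazard after cross-over or re-treatment, exponential times, administrative censoring at 48 to 70 months, and random switching at progression. Unstratified Cox models were fitted to very large simulated samples. Neither RPSFT nor IPCW was run. Censoring at the switch stands in for a perfect adjustment, so the 0.70 it returns is the input, not a finding.

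No re-treatment (about 69% of control patients progress before death or censoring):

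| Progressing control patients crossing over | Share of control arm | ITT hazard ratio | Cross-over removed |
|---|---|---|---|
| 30% | about 21% | about 0.74 | 0.70 |
| 50% | about 34% | 0.77 to 0.78 | 0.70 |
| 70% | 48% to 49% | about 0.81 | 0.70 |

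Re-treatment added, with 50% of control progressors crossing over (about 56% of the Lutathera arm progress):

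| Progressing Lutathera patients re-treated | Share of Lutathera arm | Control switchers censored only | Both arms handled alike |
|---|---|---|---|
| 20% | about 11% | about 0.69 | 0.70 |
| 40% | about 22% | about 0.67 | 0.70 |

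In the 40% row the control-only result depends on the assumed benefit after switching. It is about 0.70 with no benefit, 0.68 to 0.69 with a 15% lower hazard and 0.64 with a 50% lower hazard.

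**The case against.** The strongest reply is that little hangs on this. OS is an other-secondary endpoint, no OS hypothesis test is planned, and the hierarchy in SAP 5.4.1 stops at the quality-of-life scales. At the PFS analysis there is nothing to choose between, because SAP 2.7.1 defers RPSFT and IPCW to the final analysis. The intended label can also be inferred: the protocol, the main SAP text and SAP Section 4 agree on ITT, and protocol 8.3.3 says OS is not censored for later anti-tumor treatment. The outlier is an appendix note that the SAP revision history shows was moved in August 2023. Its notation gives the Lutathera dose in milligrams, although the study doses in GBq, which suggests text carried over from another plan.

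All of that stands, and it limits the point to a reconciliation. It does not remove the conflict. Reading the second sentence of SAP 2.7.1 as a remark about timing does not help either, because the ITT label is a separate sentence and the appendix reverses both labels.

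The illustrated shifts are also small beside sampling error. The assumptions give about 125 deaths among 222 patients, so the 95% interval multiplies and divides the hazard ratio by roughly exp(1.96/√(125 × 2/9)) = 1.45.

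**Conclusion.** Both defects are in current text. SAP 5.4.3 and 5.4.3.1 contradict SAP 2.7.1 and protocol 12.5.2 on the primary OS analysis. The re-treatment correction claimed for RPSFT and IPCW is made by neither. Following the plan as written would leave the main OS estimate unsettled and mislabel the adjusted ones.

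A reader might infer three stronger things that the documents do not support.
- That the error rate of the trial is at risk. OS carries no test, so type I error, the 99 PFS events and the 222 patients are untouched.
- That the sponsor holds two equally authoritative primary analyses to choose from. The protocol, SAP 2.7.1 and SAP Section 4 all point to ITT.
- That the IPCW result must favour Lutathera. That holds only if re-treatment prolongs survival; with no such benefit the shift is zero.

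The sizes above rest on assumed OS inputs and show only that the choice of label can matter more (up to about 0.11 on the hazard ratio) than the re-treatment gap (about 0.01 to 0.03 at a 30% benefit). The plan should be corrected, but the trial's confirmatory conclusions do not depend on it.

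**What to change.** In SAP 5.4.3 and 5.4.3.1, replace the two conflicting sentences with: *ITT is the primary OS analysis; RPSFT and IPCW are supportive.*

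Then choose one of two options.
- (a) Delete the re-treatment claim for both methods in SAP 2.7.1 and 5.4.3, and label both results *adjusted for control-arm cross-over only*.
- (b) For IPCW, censor Lutathera-arm patients at the first re-treatment dose and estimate weights in that arm as well. Still delete the re-treatment claim for RPSFT, and give that result the label in (a).

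Also correct the pointers in SAP 2.7.1, which send the reader to Section 5.4.1 for these methods; they are in 5.4.3.

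The cost is SAP wording, plus one more weight model under (b). Option (a) matches the algorithms as they stand. The edit should be made before the final analysis, when the adjusted methods are first run.

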5.4.3.1 RPSFT approach

The primary analysis of OS will be using *rank-preserving structural failure time method (RPSFT)* to correct for confounding introduced by the change of treatment (Robins and Tsiatis 1991; Korhonen et al 1999). The use of RPSFT method allows to estimate the survival time gained by anyone receiving Lutathera (i.e., either as randomized to Lutathera or after cross-over from Octreotide LAR to open-label Lutathera). The RPSFT model is based on an accelerated failure time model (Kalbfleisch and Prentice 2002) and uses a structural assumption of time-proportionality instead of a proportional hazards assumption as used in the Cox model. The widely used Cox model measures drug effect on the hazard ratio scale, whereas the accelerated failure time model measures drug effect on the survival time ratio scale.

Notation

We follow (Korhonen et al 1999) for the notation. The treatment assignment indicator is denoted by R_i and takes the value 0 if allocated to Octreotide LAR and 1 if allocated to active drug (Lutathera 10 mg). $Strata_i$ stands to baseline stratification factors. Each individual is followed from the time of randomization (DR_i) until death or the date of last contact (EOF_i) and the fixed closing date (CD_i) which ever comes first. The censoring time $C_i = \min(EOF_i - DR_i, CD_i - DR_i)$, is measured in days and is assumed to be independent of the treatment assignment. (Note: in a sensitivity analysis, censoring time $C_i = EOF_i - DR_i$ will also be considered). Time to death (T_i) is the time from randomization to death which is also measured in days. We can only observe $X_i = \min(T_i, C_i)$ with $\delta_i = 1$ if $X_i = T_i$ and $\delta_i = 0$ otherwise. Some of the subjects randomized to the Octreotide LAR arm switch to the active drug at some point after randomization. There may be several different periods when active drug has been received instead of the randomized Octreotide LAR. The total time from randomization to switch is denoted as A_i . If no switch occurs in the Octreotide LAR arm then $A_i = 0$. Switching to the active drug is potentially related to the patient's prognosis and thus cannot be assumed independent of the death time.

Thus, the observed data for each subject i are $\{R_i, Strata_i, C_i, X_i, \delta_i, A_i\}$.

Model

For subject i , we denote U_i as the potential survival time without Lutathera. U_i is a concept that is defined for each subject at the time of the randomization and U_i may depend on the value of

the baseline risk factor. U_i will be observed only for those subjects who will never receive active drug during the study and die before $\min(EOF_i, CD_i)$.

For a given time to switch A_i , the Lutathera-free survival time U_i is linked to the death time T_i through a structural model

$$U_i = \int_0^{T_i} e^{\psi A_i(s)} ds$$

where $A_i(t) = 1$ if subject i has not switched at time t and 0 otherwise. For a fixed value of the parameter ψ the above model can be written as

$$U_i(\psi) = \int_0^{A_i} e^{\psi \times 1} ds + \int_0^{T_i - A_i} e^{\psi \times 0} ds = A_i e^\psi + (T_i - A_i).$$

If $A_i(t) = 0$ for all t then $U_i = T_i$. If, on the other hand $A_i(t) = 1$ for all t then $U_i = T_i e^\psi$. Thus the parameter ψ has the following interpretation: e^ψ expresses how much the survival time is increased or decreased on relative scale if on Lutathera versus if not on Lutathera.

Therefore, we can see that the main assumption of this method is that the total duration of survival time for each patient is the sum of two distinct parts:

- potential survival time, had no Lutathera been received, and
- time added from multiplying the duration on Lutathera by an unknown factor.

For the estimation of the parameter ψ it needs to be assumed that:

1. the above model correctly captures the drug action
2. no other factor than the amount of Lutathera received, A_i , induces a difference in survival experience for an individual i under different treatment arm assignments
3. the Lutathera-free survival time U_i for an individual i is unaffected by the drug assignment or by the survival experience of other individuals
4. the censoring time C_i is independent of the randomization mechanism R_i

Estimation algorithm for parameter ψ

Randomization guarantees that any variable measured at baseline will on average be balanced with respect to the drug assignment. In particular, $U_i \perp\!\!\!\perp R_i$ where $\perp\!\!\!\perp$ denotes statistical independence. This holds also within each of the k strata of the baseline risk factor. It follows that

$$\Pr(U_i(\psi) \leq x | R_i = 0, Strata_i = z) = \Pr(U_i(\psi) \leq x | R_i = 1, Strata_i = z), \quad z = 1, 2, \dots, k.$$

In other words, the drug free survival time is independent of the randomization within the different strata of the baseline risk factor. Therefore, a procedure for estimating the parameter ψ can be based on computing $\hat{U}_i(\psi)$ for various values of ψ and finding a value $\hat{\psi}$ where $\hat{U}_i(\hat{\psi}) \perp\!\!\!\perp R_i | Strata_i$. We use the stratified log-rank test statistic for a device to estimate the

parameter ψ . The stratified log-rank test statistic is obtained from PROC PHREG procedure in SAS. The stratified log-rank test has an asymptotic chi-squared distribution with one degree of freedom under the hypothesis $\psi = \psi_0$ where ψ_0 denotes the true parameter value. From a grid

of values for ψ we choose as $\hat{\psi}$ where the stratified log-rank test statistic has its minimum value. The approximate lower and upper 95% confidence limits are obtained as those values where the stratified log-rank test statistic is close to 3.84. In reality the stratified log-rank test statistic is a step function in ψ and therefore there might be several values where the minimum is obtained and also the upper and lower confidence limits need to be chosen as the point for ψ where the value of the stratified log-rank test statistic changes from less than 3.84 to greater than 3.84.

Complication due to censoring in the estimation algorithm

One complication arises from the fact that due to censoring $U_i(\psi)$ cannot always be computed from the observed data using the above model. One cannot simply replace T_i by X_i in the above model and calculate the respective value, say $U_i^x(\psi)$ from the model because then $U_i^x(\psi)$ would not be independent of R_i and the assumptions for the estimation would not hold. Instead the censoring is handled as follows.

$$C_i(\psi) = \min(C_i, C_i e^\psi)$$

i) If $\delta_i = 1$ then calculate $X_i(\psi) = \min(U_i(\psi), C_i(\psi))$
 $\delta_i(\psi) = I(X_i(\psi) = U_i(\psi))$

$$C_i(\psi) = \min(C_i, C_i e^\psi)$$

ii) If $\delta_i = 0$ then calculate $X_i(\psi) = C_i(\psi)$
 $\delta_i(\psi) = 0$

By these definitions, $C_i(\psi)$ is independent of $U_i(\psi)$ and R_i . The new censoring time $C_i(\psi)$ can be interpreted as the maximum $U_i(\psi)$ that can be calculated which is smaller than C_i no matter how long individual i is on the randomized active drug. Both $X_i(\psi)$ and $\delta_i(\psi)$ can be calculated based on observed data and furthermore $\{X_i(\psi), \delta_i(\psi)\} \sqcup R_i \mid Strata_i$. Thus the estimation can be performed by calculating $X_i(\psi)$ and $\delta_i(\psi)$ for the various values of ψ within the different strata of the baseline risk factor and proceed as described in the estimation section.

This way of dealing with censoring was introduced by [Robins and Tsiatis 1991](#). Note that some extra censoring will occur due to nature of handling the censoring times in this estimation procedure. This causes some loss of power.

Summary of the method and interpretation

Drug effect is obtained by estimating the multiplicative factor; which would be interpreted as either a relative increase or decrease in survival if one took active drug (Lutathera) compared to taking Octreotide LAR. The multiplicative factor is determined by repeatedly reconstructing the anticipated survival duration of all patients by varying degrees of the factor, until both survival curves (Lutathera arm and Octreotide LAR) can no longer be distinguished, i.e., as if all patients only received Octreotide LAR.

This method maintains the original randomized-group definitions and thus preserves the validity of between group comparison. It provides a randomization based estimate of drug effect corrected for the bias due to crossover (under the assumption that the effect is multiplicative in time). This estimate is valid even in presence of outcome dependent drug change. Of note, this method requires extra censoring (i.e., some events become censored) which impacts the precision of the drug effect estimate.

5.4.3.2 Marginal Structural Cox Proportional Hazards Model using the Inverse Probability of Censoring Weighting (IPCW)

The Marginal Structural Cox Proportional Hazards Model using the Inverse Probability of Censoring Weighting (IPCW) will also be considered ([Hernan et al 2000](#)) to account for the treatment cross-over.

We follow [Hernan et al 2000](#) and [Korhonen et al 1999](#) for the notation. The treatment assignment indicator is denoted by R_i and takes the value 0 if allocated to Octreotide LAR and 1 if allocated to active treatment (Lutathera). The baseline covariates to be included in the model are jointly denoted as matrix V_i , containing the variables Ki67 and Karnosky score. We will consider two time-dependent covariates: Karnofsky score and investigators assessment of disease progression which are collectively denoted as matrix L_i .

Each individual is followed from the time of randomization (DR_i) until death or the last date of contact (EOF_i) and the fixed closing date (CD_i) which ever comes first. The censoring time, $C_i = \min(EOF_i - DR_i, CD_i - DR_i)$, is measured in days and is assumed to be independent of the treatment assignment and also from the death time. Time to death (T_i) is the time from randomization to death which is also measured in days. We can only observe $X_i = \min(T_i, C_i)$ with $\delta_i = 1$ if $X_i = T_i$ and $\delta_i = 0$ otherwise. The follow-up time is divided in to intervals $k=0, 1, 2, \dots, K$ where 0 denotes the baseline. The length of the intervals after baseline may vary but the same intervals are used for each individual. Some of the subjects randomized to the Octreotide LAR arm switch to the active treatment at some point after randomization. Switching to the active treatment is potentially related to the patient's prognosis and thus cannot be assumed independent of the death time. The time to switching to the active treatment is denoted by S_i and for subjects who do not switch to the active treatment arm we define $S_i = X_i$. We denote

$A_i(k) = 0$, if the subject did not receive active treatment during the time interval k and $A_i(k) = 1$, if the subject received active treatment during the time interval k . For subjects randomized to the active treatment arm $A_i(k) = 1$ for all k until X_i . Similarly, for subjects randomized to the Octreotide LAR arm $A_i(k) = 0$ for all time intervals k prior to S_i and $A_i(k) = 1$ thereafter for all k until X_i . With these notations we call $A_i(X_i) = \{A_i(u); 0 \leq u \leq X_i\}$ subjects observed active treatment until the end of follow-up and $\bar{A}_i(k) = \{A_i(u); u = 0, 1, \dots, k-1\}$ a subject's active treatment history until the start of the k^{th} time interval. The time-dependent covariate history is similarly denoted by $\bar{L}_i(k) = \{L_i(u); u = 0, 1, \dots, k-1\}$ and subjects observed time-dependent covariates until the end of follow-up as $L_i(X_i) = \{L_i(u); 0 \leq u \leq X_i\}$.

Thus the observed data for each subject i are $\{R_i, V_i, L_i(X_i), C_i, X_i, \delta_i, A_i(X_i)\}$.

The usual ITT approach for estimating the treatment effect concerning overall survival is likely to be biased towards zero due to considerable amount of switching to the active treatment in the Octreotide LAR arm. In order to trying to estimate the treatment effect one might think of estimating the time varying effect of treatment received on overall survival possibly using Cox's proportional hazards model to model the death risk as a function of the treatment history $\bar{A}_i(k) = \{A_i(u); u = 0, 1, \dots, k-1\}$. This approach is likely to be biased whenever there is a time-dependent covariate that is (i) both a risk factor for mortality and (ii) which also predicts subsequent treatment $A_i(u)$ and (iii) at the same time the treatment history $\bar{A}_i(k)$ predicts the subsequent level of the time-dependent covariate $L_i(u)$. In this study the Kanrofsky performance status after baseline, Ki67 and investigator's assessment of disease progression are such time-dependent covariates.

One approach trying to finding an unbiased estimate of the treatment effect is to use the marginal structural Cox proportional hazards model where the death risk is modeled using a conventional Cox's proportional hazards model using time-dependent case weights for those who did not switch to active treatment but continue to remain on their original randomized treatment.

The marginal structural Cox model is specified as follows:

$$\lambda(t | \bar{A}(t), V) = \lambda_0(t) \exp(\gamma_1 A_i(t) + \gamma_2 V_i); t \leq S_i$$

where a subject stays at risk for death until (s)he switches to the active treatment. Thus, the whole follow-up experience from randomization to $X_i = \min(T_i, C_i)$ is used from subjects randomized to the active treatment arm. But, in the Octreotide LAR arm only the follow-up experience from randomization to $\min(S_i, X_i)$ is used in the marginal structural Cox model. This

means in practice that in the Octreotide LAR arm the data after switching to the open label active treatment is discarded. Each subject is given in this model the case weight indicating the cumulative probability of not switching to the active treatment at time t . Unfortunately, the PROC PHREG procedure does not allow to specify time-dependent weights. Therefore one needs to divide the follow-up time into discrete time intervals and fit the above model using the PROC GENMOD procedure which allows time-dependent weights.

The case weights are estimated using the IPCW scheme for the probability of switching in the Octreotide LAR arm. In the IPCW, the probability of not switching is modeled using two separate logistic regression models as follows:

$$sw_i(k) = \prod_{u=0}^k \frac{\Pr(A_i(u) = a_i(u) \mid \bar{A}_i(u) = (0, \dots, 0)^T, V_i)}{\Pr(A_i(u) = a_i(u) \mid \bar{A}_i(u) = (0, \dots, 0)^T, V_i, \bar{L}_i(u))}$$
$$a_i(u) = \begin{cases} 1 & \text{if subject crossed - over at time } k \\ 0 & \text{if subject did not crossed - over at time } k \end{cases}$$

The first logistic regression model (i.e., the nominator model) uses only the baseline covariate information to describe the probability of switching. The second logistic regression model (i.e., the denominator model) uses both baseline covariate information and time-dependent covariate information. The estimation of these stabilized weights can easily be done with the PROC LOGISTIC procedure in SAS.

Note that the estimation of the stabilized weights is only needed in the Octreotide LAR arm. In the active treatment arm we set the stabilized weights to 1 for all subjects and for all discrete time periods.

This type of weighting effectively creates, for a risk set at time t , a pseudo-population in which $\bar{L}_i(u)$ no longer predicts the receipt of active treatment at time t (that is, $\bar{L}_i(u)$ is not a confounder). If we can be comfortable assuming that after having modeled the dependence of the subsequent treatment $A_i(u)$ with the stabilized weights then under this assumption of no unmeasured confounders, the coefficient γ_1 of $A_i(u)$ in the marginal structural Cox model represents the causal association between the receipt of active treatment and mortality on the log-hazard ratio scale.

Note: For the estimation of the stabilized weights and the discrete version of the marginal structural Cox model one has to model the time-dependent intercepts using either a smooth function of time, such as a cubic spline or by combining time intervals. Otherwise the estimation may not be possible and also the asymptotic theory may break down.

